## **Statement of Compliance**

The study will be carried out in accordance with Good Clinical Practice (GCP) as required by the following:

- U.S. Code of Federal Regulations applicable to clinical studies (45 CFR 46)
- 21 CFR 312
- ICH GCP E6
- Completion of Human Subjects Protection Training
- NIH Clinical Terms of Award

PI	Principal Investigator
SAE	Serious Adverse Event/Serious Adverse Experience
SMC	Safety Monitoring Committee
SOP	Standard Operating Procedure
SPR	Surface Plasmon Resonance
WHO	World Health Organization

---

# 1 PROTOCOL SUMMARY

**Title:** Evaluation of the effects of age, prior exposure and previous vaccination on the B cell response to inactivated influenza vaccine in healthy adults and children.

**Population:** 240 Healthy adults and children ages 9 and over

**Number of Sites:** Single site study

**Study Duration:** 5 years

**Participant Duration:** 6 months

## **Objectives:**

### **Primary Objective**

To evaluate the relationship between first influenza A virus exposure (inferred by age), vaccine history, and baseline serum antibody response to seasonal influenza vaccine in healthy adults and children.

### **Primary Endpoint:**

- Measurement of the magnitude and specificity of the serum antibody responses by hemagglutination (HAI) and microneutralization (MN) at day 7 and 28, overall and stratified by age group, vaccine history, and baseline serum antibody level.
- 
- Serum antibody response on day 90 after vaccination by HAI and MN overall and stratified by acute antibody response.

### **Secondary Objectives**

Evaluate factors related to failure of vaccine to provide protection against symptomatic influenza and the immune response to infection in vaccinated individuals by prospective surveillance of the vaccine cohort.

**Secondary Endpoints**

Description of demographic and clinical characteristics and immune response to vaccination among subjects who develop symptomatic influenza (Vaccine Failures) and among subjects who do not.

[figure not shown]
**Exploratory Objective**

To evaluate the relationship between first influenza A virus exposure (inferred by age), vaccine history, and Memory B cell (MBC) specificity, and the magnitude and breadth of the subsequent B cell response to seasonal influenza vaccine in healthy adults and children.

**Exploratory Endpoints**

- Frequency and specificity of peripheral blood antibody secreting cells (ASC) on day 7 post vaccination (initial response), overall and stratified by age group, vaccine history, and baseline serum antibody level
- Frequency and specificity of peripheral blood memory B cells (PMBC) on day 28 post vaccination (memory response), overall and stratified by age group, vaccine history, and baseline serum antibody level

**Schematic of Study Design:**

\* Note: For children weighing less than 100 lbs, only 15 mL of blood will be drawn at each time point and plasma will be used for antibody testing. Subjects will be queried regarding any blood being drawn for other purposes such as clinical testing, and that the total drawn will not exceed the above amounts

In addition, beginning on day 48, subjects will be contacted by phone once every two weeks during the influenza season and asked about influenza symptoms. Subjects who report symptoms will be asked to return for a clinic visit and specimen collection. Influenza season will be defined as when community laboratories detect 4 or more positives in any one week for two weeks in a row.

## **3 BACKGROUND INFORMATION AND SCIENTIFIC RATIONALE**

### **3.1 Background Information**

Inactivated influenza vaccines (IIVs) have been in use in the US and worldwide for the prevention of illness due to seasonal and pandemic influenza since their licensure approximately 60 years ago. Multiple studies over many years have evaluated the immunogenicity of these vaccines in various populations. In general, serum antibody responses to IIV are vigorous in healthy young adults with low levels of pre-vaccination antibody. Nasal antibody responses can also be detected, although they are not as vigorous as those seen after live vaccination.

The serum antibody response to IIV is impacted by several factors, including the age of the subject, the presence of chronic diseases, and the use of immune modulating drugs. In addition, the prior exposure of the subject to influenza vaccine or infection appears to have a substantial impact on both the immune response as well as the protective efficacy of IIV. For seasonal influenza vaccine, the magnitude of the serum antibody response is lower in individuals who begin with higher titers, and highest in those with low prevaccination titers. Consistent with this observation, individuals with prior vaccination, and who therefore have higher baseline antibody titers, tend to have less vigorous antibody responses to revaccination. The impact of prior vaccination on protection is controversial. Some studies have suggested that vaccine efficacy is higher in those who were not vaccinated in the previous season than in those who were [1, 2]. Other studies have not seen this association [3]. The mechanisms by which prior exposure to vaccine or infection might modify the subsequent response to IIV are not known, but would have obvious implications for the design of new influenza vaccines and vaccine strategies.

### **3.2 Scientific Rationale**

This protocol will address the hypothesis that vaccination and infection drive adaptation of the antibody secreting and memory B cell populations, and differ based on the antigenicity of the vaccine strains and immune history of the subject. This protocol will address whether initial influenza priming, most likely occurring during childhood, affects later-in-life immune responses to influenza vaccination. Recent data in the literature [4, 5], and our own preliminary data suggest that initial encounters with influenza have a long lasting effect on circulating antibodies and the specificity of the memory B cell repertoire. This protocol will test whether qualitative and quantitative differences in circulating antibodies and memory B cells can strongly influence subsequent immune responses to seasonal influenza vaccines. This protocol will perform

---

parallel assessment of antibody, ASC, and memory B cells over the course of an immune response to determine how vaccination modifies the B cell and antibody repertoires. As a measure of the cells responding to the vaccination, our assays will focus on the acutely activated antibody-secreting B cells (ASC, plasmablasts) and antibodies secreted (day 7). Because these ASC can be short lived, later in the response this protocol will also look at in vitro reactivated memory B cells and secreted antibodies at days 0, 28, and 90 as measures of the adapted responses before and after vaccination. Serum antibodies will also be tested for function, specificity, amount, and quality by conventional HAI and MN assays, as well as more sophisticated assays described below (ELISA, SPR, GFPDL).

### **3.3 Potential Risks and Benefits**

#### **3.3.1 Potential Risks**

The risks and discomforts of this study include risks associated with the vaccine, administration of the vaccine, the risks associated with study procedures (blood drawing and nasal and throat swabs) and possible loss of confidentiality.

In placebo-controlled trials in adults, inactivated seasonal vaccines are associated with mild local pain at the site of administration. Systemic symptoms like fever and malaise occur at rates equal to placebo. According to the [REDACTED] package insert, in adults, the most common ( $\geq 10\%$ ) injection site adverse reaction was pain (36%); the most common systemic adverse events were muscle aches (16%), headache (16%), and fatigue (16%). In children aged 3 through 17 years, the injection site adverse reactions were pain (44%), redness (23%), and swelling (19%). In children aged 3 through 5 years, the most common ( $\geq 10\%$ ) systemic adverse events were drowsiness (17%), irritability (17%), and loss of appetite (16%); in children aged 6 through 17 years, the most common systemic adverse events were fatigue (20%), muscle aches (18%), headache (16%), arthralgia (10%), and gastrointestinal symptoms (10%).

During the swine influenza vaccine campaign of 1976, about 10 per 1,000,000 vaccine recipients in excess of the background rate developed the paralytic illness called Guillain-Barré Syndrome (GBS). In the subsequent decade, no association between seasonal influenza vaccine and GBS was found. More extensive investigations of this potential association occurring in the 1990s revealed that there was a small but detectable risk of GBS in the 6 weeks following seasonal influenza immunization: an attributable risk of approximately 1 per 1,000,000, adjusted for potential confounders. In the period since the Vaccine Adverse Event Reporting System (VAERS) was established in 1990, the rates of GBS reports following influenza vaccination have declined substantially. The annual reporting rate in that period was highest in the 1993-1994 influenza season (1.7 per 1,000,000 vaccinees) and lowest in the last season analyzed in the report, 2002-2003 (0.4 per 1,000,000 vaccinees) [6]. No cases of GBS have

been reported following receipt of novel H1N1 influenza vaccines to date, but the total number of recipients is only in the thousands. Most persons who develop GBS recover completely.

Drawing blood causes transient discomfort and may cause fainting. Bruising at the blood draw site may occur but can be prevented or mitigated by applying direct pressure to the draw site for several minutes. The use of alcohol swabbing and sterile equipment will make infection less likely at the site where blood will be drawn. Nasal and throat swabs can be uncomfortable and may cause gagging.

Personal health information of the subjects will be collected to determine eligibility and to evaluate safety and reactogenicity outcomes throughout the study. Research personnel will make every effort to keep this information confidential. Still, a risk of participation is that the confidentiality of this information could be lost.

### **3.3.2 Known Potential Benefits**

Administration of licensed vaccines for seasonal influenza is recommended for all children and adults and would be expected to provide partial protection against influenza illness caused by the strains contained within the vaccine.

## **4 OBJECTIVES AND OUTCOME MEASURES**

### **4.1 Study Objectives**

#### **Primary Objective**

To evaluate the relationship between first influenza A virus exposure (inferred by age), vaccine history, and baseline serum antibody response to seasonal influenza vaccine in healthy adults and children

#### **Secondary Objectives**

- Evaluate factors related to failure of vaccine to provide protection against symptomatic influenza and the immune response to infection in vaccinated individuals by prospective surveillance of the vaccine cohort.

#### **Exploratory Objectives**

---

Evaluate the relationship between first influenza A virus exposure (inferred by age), vaccine history, and Memory B cell (MBC) specificity, and the magnitude and breadth of the subsequent B cell response to seasonal influenza vaccine in healthy adults and children

## 4.2 Outcome Measures

### Primary Outcome Measures:

- Measurement of the magnitude and specificity of the serum antibody responses by hemagglutination (HAI) and microneutralization (MN) at day 7 and 28, overall and stratified by age group, vaccine history, and baseline serum antibody level
- Serum antibody response on day 90 after vaccination by HAI and MN and overall and stratified by acute antibody response

### Secondary Outcome Measures

- Description of demographic and clinical characteristics and immune response to vaccination among subjects who develop symptomatic influenza (Vaccine Failures) and among subjects who do not.

### Exploratory Outcome Measures

[figure not shown]
- Frequency and specificity of peripheral blood antibody secreting cells (ASC) on day 7 post vaccination (initial response), overall and stratified by age group, vaccine history, and baseline serum antibody level
- Frequency and specificity of peripheral blood memory B cells (PMBC) on day 28 post vaccination (memory response), overall and stratified by age group, vaccine history, and baseline serum antibody level

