B cell responses: Our previous studies have shown that the antibodies secreted by activated B cells (plasmablasts) and re-activated memory B cells have different specificities and affinities that those that accumulate in the serum. In addition, there is evidence from analyzing secreted antibodies that vaccination affects the specificities and improves affinities. Therefore, the studies of antibody-secreting (ASC) and memory B cells require the collection of Peripheral Blood Mononuclear Cells (PBMC) at different times before and after vaccination for analysis. PBMC will be obtained before and on days 0, 7, 28, and 90 after vaccine and evaluated for B-cell responses. First, antibody secreting cells stimulated by the vaccination, which peak 7 days after vaccination in the blood, will be analyzed by performing B cell ELISPOT assays on plates coated with recombinant HA proteins that match the influenza strains in that year's vaccine. In addition, supernatants will be collected from cultured plasmablasts for analysis by HAI, MN, and ELISA as described above. Memory B cell responses will be assessed similarly at all the time points by reactivating the B cells in culture [7], performing B cell ELISPOT assays and collecting culture supernatants for analysis as described above. The analysis of the ASC and

memory B cells provides a measure of how the vaccine modifies the B cell repertoire, as well as how well someone is responding to the vaccine.

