### **12.2 Sample Size Considerations**

Because the degree of variability in many of the measurements in this study are unknown, estimating the precision of the correlation of patient characteristics (age and prior vaccination history) with outcomes (antibody quality and quantity and B cell response) is not possible. The

---

study will evaluate these outcomes and if trends towards a relationship are discovered subsequent studies will evaluate these in more detail.

However, the precision of the estimate of the proportion of subjects who achieve a pre-specified number of memory B cells specific for any antigen on day 28 would be determined by the number of subjects. If there were 30 subjects in any particular age strata, then the half-width of the 95% confidence interval for the estimate of the the proportion achieving any level of mBC in that strata is shown below

No. of subjects	Proportion achieving mBC frequency	Half-width of the 95% CI for estimate of proportion
30	10%	10.7%
30	20	14.3
30	30	16.4
30	40	17.5
30	50	17.9

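### The memory B cell outcome is a day-28 level with no use of the day-0 value, so differences by age or vaccine history would mix pre-existing memory with vaccine-induced response

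*Combined protocol and SAP*

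**What the plan says.** The outcome, worded alike in the Protocol Summary and in section 4.2, is "Frequency and specificity of peripheral blood memory B cells (PMBC) on day 28 post vaccination (memory response), overall and stratified by age group, vaccine history"; the sentence goes on to name baseline serum antibody level as the third stratifier. The day-7 antibody-secreting cell (ASC) outcome has the same three stratifiers. Neither outcome mentions a day-0 MBC value.

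Section 12.2 takes the same view of the endpoint. Its precision table is for "the proportion of subjects who achieve a pre-specified number of memory B cells specific for any antigen on day 28", with 30 subjects per age stratum. Section 12.4, the final analysis plan, is one sentence on when data will be analysed. It names no model, contrast or baseline adjustment.

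Other sections give day-0 MBC a role:

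- The exploratory objective (section 4.1) concerns the relationship between first influenza A exposure, "vaccine history, and Memory B cell (MBC) specificity, and the magnitude and breadth of the subsequent B cell response to seasonal influenza vaccine". MBC specificity stands there on the predictor side.
- Section 12.1 has the HA-specific B cell response depend on age, vaccine history and baseline B cell reactivity.
- Section 3.2 plans to study "in vitro reactivated memory B cells and secreted antibodies at days 0, 28, and 90 as measures of the adapted responses before and after vaccination".
- Section 9.2.1 states that "Memory B cell responses will be assessed similarly at all the time points by reactivating the B cells in culture", and section 8.1 draws blood for mononuclear cells at baseline.

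**The concern.** Age and vaccine history are studied because earlier priming is thought to shape the memory repertoire a subject brings to vaccination; section 3.2 says as much. Those factors are therefore expected to shift the day-0 MBC level. A day-28 level contains the day-0 level plus whatever the vaccine added, so two age groups could differ on the outcome with identical responses to vaccine. They could also look alike with different responses.

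The second gap is on the predictor side. The objective asks how existing MBC specificity relates to the later response, but the ASC and MBC outcomes are stratified by baseline serum antibody instead. At stake is whether the exploratory results answer the question the protocol asks, not any confirmatory test.

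**Working it through.** **Inputs.** From the documents: n = 30 per age stratum (sections 6 and 12.2), 95% intervals, and the five half-widths in section 12.2. Not in the documents: the SD of MBC frequency, the day-0/day-28 correlation, the share of subjects above any threshold at day 0, and the correlation of serum antibody with MBC. Section 12.2 itself says the variability of many measurements is unknown. All such values below are assumptions.

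**1. The plan's own table.** Half-width = 1.96 × √(p(1−p)/30). For p = 10, 20, 30, 40 and 50% this gives 10.74, 14.31, 16.40, 17.53 and 17.89 points. The plan states 10.7, 14.3, 16.4, 17.5 and 17.9. The table reproduces, and it describes one proportion, in one stratum, at one time.

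**2. A vaccine that does nothing.** If MBC do not change, the day-28 proportion equals the day-0 proportion. With 20% above the threshold beforehand, the outcome reads 20% ± 14.3 points. For two strata of 30, the probability of a two-sided 5% difference is

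Φ{[|p1−p2| − 1.96√(2p̄(1−p̄)/30)] / √[(p1(1−p1)+p2(1−p2))/30]}.

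For 20% v 50%: p̄ = 0.35, the null standard error is 0.1232 and the alternative standard error is 0.1169, so Φ[(0.30 − 0.2414)/0.1169] = Φ(0.50) = 69%.

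| Above threshold at day 0 | P(difference), no vaccine effect |
|---|---|
| 20% v 30% | 14% |
| 20% v 40% | 39% |
| 20% v 50% | 69% |
| 10% v 50% | 94% |

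**3. Identical rise, different start.** Assume a day-28 log10 SD of 0.5 and a cut-off at the lower group's day-28 median. The lower group is then at 50% and the other at Φ(gap/0.5). The half-width for the difference is 1.96 × √[(0.25 + p(1−p))/30].

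| Baseline gap (log10) | Higher group | Difference | Half-width of difference |
|---|---|---|---|
| 0.15 | Φ(0.3) = 61.8% | 11.8 | 24.9 |
| 0.30 | Φ(0.6) = 72.6% | 22.6 | 24.0 |
| 0.45 | Φ(0.9) = 81.6% | 31.6 | 22.6 |

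Only the largest assumed gap exceeds the half-width of its own difference.

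**4. What the serum stratifier removes.** With a linear correlation ρ between baseline serum antibody and baseline MBC, the share of MBC variance left is 1 − ρ²: 96, 84, 64 and 36% at ρ = 0.2, 0.4, 0.6 and 0.8. Section 9.2.1 reports that antibodies from reactivated memory B cells differ in specificity and affinity from those in serum, so a perfect proxy is not expected.

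**5. Precision once day 0 is used.** Half-widths for a stratum of 30, in SD units, with equal SDs at both visits and r the day-0/day-28 correlation: raw day 28 is 1.96/√30 = 0.358; change is 0.358 × √(2(1−r)); adjusted for day 0 is 0.358 × √(1−r²).

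| r | Raw | Change | Adjusted |
|---|---|---|---|
| 0.3 | 0.358 | 0.423 | 0.341 |
| 0.5 | 0.358 | 0.358 | 0.310 |
| 0.7 | 0.358 | 0.277 | 0.256 |
| 0.9 | 0.358 | 0.160 | 0.156 |

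The adjusted analysis is never less precise than the raw level here; the change is less precise when r is below 0.5. The 12.2 table gives the precision of neither.

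**The case against.** The strongest reply is that the before/after comparison is plainly intended. Day-0 cells are drawn and assayed, section 3.2 describes days 0, 28 and 90 as before and after measures, and section 12.1 names baseline reactivity. A reader might infer from the outcome wording that baseline MBC can never be related to the response, or that pre-existing memory will be reported as vaccine response. The documents support neither: the data will exist, and no section states such an analysis. What stands is narrower. No outcome takes the comparison up, and section 12.4 does not fill the gap.

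A reader might also take section 12.2 to define a responder. It does not; it illustrates precision and says trends will be pursued in later studies. Nor may the 23-point illustration be set against the 10.7 to 17.9 points in that table, which are for a single stratum. Against the half-width of a difference, 24.0 points, it falls just short.

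The identical-rise assumption can be questioned too. Section 3.1 says serum responses are lower in those who start high; if MBC behave likewise, the day-28 gap would shrink. That makes the size uncertain, but a level would still not show the response. Finally, baseline serum antibody is a genuine, partial stratifier, and the outcome is exploratory in a single-site study with no confirmatory test. Both points limit the weight of the concern without removing it.

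**Conclusion.** The concern holds as a mismatch inside the protocol. The MBC outcome and the 12.2 table use a day-28 level, while the objective, the hypothesis, the rationale and the assay section call for day-0 MBC as reference or predictor. Differences in the stated outcome by age or vaccine history would combine pre-existing memory with vaccine-induced response. That conclusion needs only the outcome definition and the protocol's own expectation that immune history shapes baseline memory.

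The size cannot be fixed from the documents. Across the assumed ranges, the spurious difference runs from 12 to 32 points for an identical rise, and the chance of a nominally significant difference with no vaccine effect runs from 14% to 94%. The point is worth correcting before the MBC data are analysed. It does not touch the serum antibody primary outcomes.

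**What to change.** 1. In the Protocol Summary and section 4.2, make the main analysis of the MBC outcome the day-28 log antigen-specific MBC frequency adjusted for its day-0 value (an ANCOVA-type model). Report the day 0 to day 28 change descriptively. State the value assigned to undetectable frequencies, since their log is undefined.
2. Add baseline MBC frequency and specificity as a predictor or stratifier for the day-7 ASC and day-28 MBC outcomes. Do not regress the change on its own baseline: baseline then sits on both sides, and assay error alone produces a negative association.
3. In section 12.2, either label the table as the precision of a day-28 level or restate it for the baseline-adjusted quantity over a range of assumed correlations.

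**Cost.** The change is to wording and the precision statement; the blood draws and assays are already planned. Subjects without a usable day-0 MBC result drop out of the adjusted analysis. Adjustment and change also answer different questions when groups start apart. With equal SDs and an identical rise, the adjusted comparison still shows (1 − r) × the baseline gap: for 0.3 log10, 0.09 at r = 0.7 and 0.21 at r = 0.3. The text should therefore say that the adjusted result compares subjects with the same day-0 level, and show the descriptive change beside it.
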